6.2. Selection of participants and strategies for recruitment	36
6.3. Eligibility evaluation	36
6.4. Study Procedures for Visits and Contacts	37
6.4.1. General summary of the study per visit	37
6.4.2. Clinical files (CRF) per visit and visit windows.	39
7. Control and active search for defaulters	44
7.1. Strategies for retention of study participants	45
8. Quality control and quality assurance of the study	45
8.1. Study Coordination	45
8.2. Internal study monitoring group	45
8.3. Quality assurance	46
9. Protecting study participants	47
9.1. Confidentiality	47
9.2. Risks	47
9.3. Benefits	48
9.4. Research Ethics Committee	48
9.5. ANVISA	48
10. Good Practices	48
11. Publications	48
12. Record and data management	49
13. Expected outcomes	49
14. Execution Schedule:	50
15. Bibliography	51

Executive Summary

Objective	Estimate the safety and performance of mammary implants with a textured surface and mammary implants with a polyurethane foam-coated surface of the brand Silimed® already available in the market
Primary Objective	Estimate the risk / rate of known and unexpected adverse events of short and long term for each type of implant Silimed®.
Secondary Objective	Estimate the performance of implants through satisfaction and quality of life after placement of the Silimed® breast implant.
Design	Phase IV clinical trial, open, non-randomized (or quasi-experimental) prospective trial.
Location	Brazil – Rio de Janeiro – Rio de Janeiro
Participants, inclusion and exclusion criteria	Consecutive inclusion within the recruitment period up to the estimated minimum sample size. Inclusion criteria: (1) provide written free and informed consent, (2) female at birth, (3) aged 18 years or older, (4) have received breast implant(s) up to 14 days prior who sought primary breast augmentation, (5) have received breast implants with textured surface or breast implants with polyurethane foam-coated surface of the brand Silimed®, (6) ability to comply with the protocol for the entire follow-up time. Exclusion criteria: (1) secondary breast augmentation (2) gestation or breastfeeding, (3) advanced fibrocystic disease at the time of implantation, (4) neoplasia of any type not yet treated or being treated at the time of implantation, (5) infection in activity not yet treated or in treatment at any site at the time of implantation, (6) reporting or recording of adverse reactions or intolerance to polyurethane or silicone prior to implantation, (7) immune diseases that affect connective tissue in activity or in treatment (e.g., lupus erythematosus, discoid lupus, scleroderma, etc.) at implantation, (8) signs of inflammation of the breast or implant site at implantation, (9) high surgical risk or complications in the immediate postoperative period prior to implantation, (10) drug use prior to implantation that increase the risk of immediate postoperative complications (e.g., medicines that interfere with coagulation), (11) may not have participated in another clinical trial up to 6 months prior to implantation, (12) any other condition that, based on the investigator or designee, may prevent the provision of informed consent, renders study participation unsafe, compromises adherence to the protocol, complicates the interpretation of data from the study outcome, or otherwise interferes with the achievement of study objectives.
Exposure / intervention of major	Silicone breast implant of the brand Silimed® (breast implants with textured surface and breast implants with polyurethane foam-

Silimed Indústria de Implantes Ltda

[name]

[contact] **[contact]

www.silimed.com.br • [contact] • facebook: silimed international/brasil

interest	coated surface of the brand Silimed®).
Primary outcomes	Expected or unexpected adverse events during the follow-up period. Examples of expected adverse events (but not restricted): asymmetry, breast pain, tissue atrophy, calcification, capsular contracture, rupture, delay in wound healing, extrusion, hematoma, infection, inflammation or irritation, lymphedema or lymphadenopathy, displacement, necrosis, anesthesia, hypoesthesia, paraesthesia or hyperesthesia of the breast or nipples, palpability, ptosis, ecchymosis, seroma, skin rash, visibility, wrinkling and undulation, cysts and nodules. The events of greatest interest initially are the events that cause the need for any reoperation, removal of the implant, removal of the implant with replacement or removal of the implant without replacement, events directly related to the presence of the implant (capsular contraction grade III / IV, implant, etc.).
Secondary outcomes	Breast self-assessment questionnaire (BEQ-Brazil), Rosenberg global self-esteem scale, patient satisfaction, researcher satisfaction.
Duration of the study	Each participant will be followed up to 10 years.
Allocation of treatment	As the participants will be invited to participate after the implants, the research protocol does not foresee any interference of the research procedures in the choice of the type or size of the implants as well as in the surgical technique used.
Masking / Blinding	There will be no masking / blinding.
Statistical analysis plan	For the primary endpoint, the risk / rate of groups of adverse events and specific events and their respective confidence intervals. These estimates will be made taking into account both the implant and the patient as unit of observation. For the secondary objectives changes in scores over time will be used to construct gross and adjusted correlation trajectories.
Minimum Sample	700 participants divided into 2 groups formed by the type of implant. There will be 350 volunteers with implants with textured surfaces and another 350 with implants with polyurethane surface.
Intermediate analysis	They will always occur once a year for the duration of the study. Interim analyzes shall consist of the same analyzes provided for in the analysis plan for the final report, unless there is sufficient sample size. Safety alarms will occur if there are a number of events (capsular contracture, implant removal with replacement or removal of the implant without replacement) more than expected. All analyzes should have a significance of 1%. In this case, the need for further analysis of specific rates and possible need for corrective measures will be assessed.

Silimed Indústria de Implantes Ltda

[name]

[contact] [contact]

www.silimed.com.br • [contact] • facebook: silimed international/brasil

1. Team

Scientific Team:

- [name] - CPF: [name] - Affiliation: *Instituto do Câncer do Estado de São Paulo. Divisão de Cirurgia Plástica do Hospital das Clínicas da Faculdade de Medicina da USP.*
- [name] - CPF: [name]- Affiliation: *Instituto Nacional de Infectologia - INI / Fundação Oswaldo Cruz - Fiocruz*
- [name] - CPF [name] - Affiliation: SILIMED Indústria de implantes LTDA
- [name] - CPF: [name] - Affiliation: SILIMED Indústria de implantes LTDA

Scientific Consultant:

- [name] - CPF: [name] - Affiliation: *Instituto do Câncer do Estado de São Paulo. Divisão de Cirurgia Plástica do Hospital das Clínicas da Faculdade de Medicina da USP.*
- [name] - CPF: [name]- Affiliation: *Instituto Nacional de Infectologia - INI / Fundação Oswaldo Cruz - Fiocruz*

Responsible for the elaboration of the research protocol:

- [name]
- [name]
- [name]

Representatives:

- *Industrial Director:* [name]
- *Research and Development Manager:* [name]
- *Regulatory Affairs and Quality Manager:* [name]
- *Research and Development / Clinical Research Coordinator:* [name]

Epidemiologist

- [name]

Statistics and Data Management

- [name] (Supervision)
- [name] (Supervision)
- Coreware (Execution)

Study Coordination Committee:

- [name]
- [name]

2.1. State of the Art

Saline and silicone breast implants have become available in the market for breast reconstruction and aesthetic indications since the 1960s. Since then, due to regulatory discussions, implants have been restricted to indications for breast reconstruction only and released after evidence accumulation at Respect for its effect and safety. [1] Even with the concerns of academia and regulatory agencies regarding safety and evidence regarding the risk of different complications, it is estimated that in the United States alone, more than one million two hundred thousand implantations occurred between the 1970s and 1980s [2] with an increasing trend since then. [3]

Over time, different types, contents, contours, shapes and size of implants appeared, always with the purpose of increasing the aesthetic result and reducing the risks of complications attributable to the implant and the related surgical act. There were also a number of surgical techniques for the same purpose, such as different accesses, reduction of the incision, addition of the patient's own tissues in the implant shop, change of store location, etc. Even so, implants need to be revised, since they generally have an estimated useful life of approximately 10 years, and may require periodic replacement. Still, once having used an implant, even without complications, the breasts are unlikely to return to satisfactory aesthetic appearance if the implant is removed for any reason.

In addition to primary reconstruction and primary augmentation, other indications and special situations unfolded and evidence with these situations also accumulated over time. Examples of such situations are reconstruction and secondary augmentation implants, gestation and breastfeeding in women with implants, radiotherapy in women with implants, recrudescence or recurrence of neoplasia in women with implants, multiple aesthetic interventions performed at the same time as implantation, etc. All these conditions could at first modify the safety and efficacy of implants when compared to primary increase.

The major concerns surrounding the use of breast implants have always been their safety. [4] Already in the 1990s, the Food and Drug Administration (FDA) has classified the complications attributable to breast implants in local and systemic. The local complications would be implant rupture (with or without gel migration), breast or thoracic pain, capsular contracture, changes in nipple sensitivity, delay in surgical wound healing, hematoma, galactocele or galactorrhea, displacement or **Silimed Indústria de Implantes Ltda**

extrusion, interference in performance or interpretation of mammograms and seroma. The systemic complications potentially involved would be autoimmune diseases (connective tissue diseases) and neoplasms (not necessarily breast). [1,4]

2.2. Expectation of beneficial effects

There is evidence showing that reduction in mortality of women who received implants after mastectomy [5-7] or after primary enlargement, [5,8] even when adjusted for prognostic factors such as age, social conditions, type, site, size and stage of neoplasia . However, other possible ways to measure the beneficial effect of breast implants for both primary mammary enlargement and reconstruction after mastectomy have emerged. Traditional outcomes focusing on morbidity and mortality are important but are no longer sufficient for a more comprehensive understanding of the effect of the implant.

The immediate and long-term beneficial effect expected is the satisfaction of the woman, which is in some way related to self-esteem, preoccupation with the image itself, which in turn has a relevant impact, although difficult to measure, in the style and in the quality of life. Therefore, numerous instruments for measuring these dimensions were applied, developed for this purpose. [9] Even so, hardly a single instrument could capture all the dimensions in the life of a person where implantation could have some effect. In the Allergan Pivotal study over 7 years, approximately 9 out of 10 women underwent primary augmentation or revision review with NATRELLE 410 Breast implants that answered the satisfaction question were definitely or a little satisfied with their breast implants.

2.3. Expectation of expected adverse events

Technical reports provided by the FDA used for silicone breast implant registries from different manufacturers indicate a variety of risks from implant or surgery-related events. The most frequent event in all reports, consistent with the literature in general, is capsular contracture. Capsular contracture, when intense, is also the most frequent indication of implant removal. Below is a comparison of risks of events of interest by major interest groups and by different manufacturers. However, it is not possible, through the data from these reports to verify if there are differences between the different types of implants, nor what prognostic elements determine

Silimed Indústria de Implantes Ltda

[name]

[contact] **[contact]

www.silimed.com.br • [contact] • facebook: silimed international/brasil

the events in the different interest groups.

Cumulative incidence by type of event, implantation indication and implant brand (data retrieved from technical registration reports).

	Natrelle (Textured Surface - in 7 years)%		Natrelle (Textured Surface - in 3 years)%		Sientra (any surface - in 3 years)%		Mentor (any surface - in 3 years)%	
Event	Augmentation	Reconstruction	Augmentation	Reconstruction	Augmentation	Reconstruction	Augmentation	Reconstruction
Any Complication	31,0	53,0	-	-	-	-	-	-
Any Reoperation	22,4	45,2	12,7	21,0	12,6	34,9	15,4	27,0
Removal of the implant with or without replacement	12,6	29,3	-	-	-	-	-	-
Removal of the implant without replacement	1,2	5,3	0,5	2,9	1,2	7,0	2,3	5,7
Removing the Implant with Replacement	11,5	25,2	5,0	14,9	4,6	19,1	2,8	7,4
Capsular contracture grade III / IV	6,1	10,7	2,1	7,3	6,0	8,8	8,1	8,3
Implant rupture	6,9	8,9	1,3	0,0	3,0	0,0	0,0	0,0

Although there is a perception that polyurethane coated implants present a lower risk of various complications (e.g. capsular contracture), lack of evidence with a direct comparison and differences in methods and follow-up times in textured surface implant studies and studies with Polyurethane surface, as well as the difference in the quality of the evidence for this comparison hinders a conclusion regarding the safety of these two types of implant.[10] However, there is evidence that some types of implants may present minor risks (particularly when compared to first generation smooth surface implants) of certain events (e.g., capsular contracture) in certain populations. [11-15]

Silimed Indústria de Implantes Ltda

[name]

[contact] [contact]

www.silimed.com.br • [contact] • facebook: silimed international/brasil

Regarding the most common expected adverse event, capsular contracture, several questions can be posed as: it is an event that can be progressive with compromised aesthetic outcome, which is surgical treatment with removal of the implant in advanced progressions and frequently occurs in the first 3 years after implantation. There is sufficient evidence showing different strategies that may reduce capsular contracture in the short term, such as: use of textured implants (compared to smooth implants), [14,15] capsule irrigation with antibiotics prior to implant placement, [16,17]] Use of preferred surgical techniques, [18] use of non-talc gloves for manipulation of the implant, prophylaxis of surgical infection with antibiotics. The advantage of implants with textured surface compared to smooth surface implants is however evident only for capsular contracture [15] and short / medium term. [14]

Regarding possible systemic events in the use of implants, the academy and regulatory authorities worry or worry about specific conditions that have arisen over time. Among them, connective tissue diseases, neoplasia (especially anaplastic giant cell lymphoma - ALCL), and suicide.

Between the 1980s and 1990s, connective tissue diseases were a major concern due to the diversity of case reports and even judicialization. [19] However, after several studies and initiatives to clarify this issue related to implants, several investigations have pointed to an absence of evidence of a causal relationship between breast implants and classic diseases of the connective tissue.[20]

In addition, suicide has been and seems to be currently a recurring issue. There is evidence of epidemiological studies indicating an excess risk of suicide among women receiving breast implants. [21,22] There is also evidence that this population differs in some characteristics of the general population or of women who do breast reduction [23,24] including psychiatric conditions prior to implantation, use of alcohol and drugs. [23,24] Although there is a strong and consistent connection between breast implant and suicide, the causal connection is quite controversial [4] and there are recommendations for evaluations Psychological aspects prior to implantation to better address previous problems. [25]

The ALCL associated with the breast implant is a distinct type of T cell lymphoma that appears in the periphery of breast implants and apparently always involved with the presence of implants with textured surface. [26] Morphological investigations indicate that a chronic inflammatory process at the periphery of the implant, even if imperceptible to clinical examination, is the main phenomenon. ALCL is generally defined as a T-cell lymphoma that has continuity with the implant or a capsule scar,

Silimed Indústria de Implantes Ltda

[name]

[contact] [contact]

www.silimed.com.br • [contact] • facebook: silimed international/brasil

composed of pleomorphic cells that express CD30 uniformly and unpublished genetic anaplastic knockout or 2q23 chromosome of anaplastic kinase. [3,26] Despite being considered a serious condition with high morbidity, ALCL is a curable disease in the vast majority of cases, with a median survival of 93% and 89% at 3 and 5 years, respectively. The ALCL presentation is variable but is commonly associated with a peri-implant late seroma, is diagnosed on average 10 years after implantation and apparently has no preference for indication group (reconstruction or increase). [3,26] The number of cases identified each year is increasing since 1986. [26] The incidence of ALCL related to the implant from population data is higher than the incidence of ALCL in breast in the general population, and is higher than was believed until 2005. [3] However, this data is controversial when compared to the incidence in very long follow-up studies (30 years or more) of women who received an implant, where the incidence is similar to the incidence of the general population. Even so, the incidence is very low and was estimated as 1 case for every 30,000 textured surface implants. [3]

The evidence in the literature regarding the safety of silicone implants is vast and comes from a number of long-term retrospective and prospective studies. In most of the events considered, there is a consistent demonstration that the incidence of events is low, both for short and long-term events after implantation, which does not lead to removal or re-surgery for correction. [4]

3. Justification

Medical device manufacturers are routinely audited and requested to ensure the best current quality standards, to update the device's research plan and to provide updated efficacy and safety related documentation when requested by the competent authorities. When new events possibly related to devices are recorded or events already known concern the authorities and the scientific community as to their severity or the increase in their incidence, new clinical research may be necessary to specifically elucidate if these unwanted events are in fact related with the medical device. These studies are termed post marketing or phase 4 safety studies. For example, in the 1990s, silicone breast implants were suspected to be related to connective tissue diseases, and several investigations were conducted in an attempt to find this relationship [29], and more recently concern has arisen that breast implants may be related to anaplastic giant cell lymphoma (ALCL). [30] Other situations in which new clinical research is justified occur when the product is indicated for new conditions, or for a population with different characteristics of the original, or as a post-marketing strategy to verify the

Silimed Indústria de Implantes Ltda

[name]

[contact] **[contact]

www.silimed.com.br • [contact] • facebook: silimed international/brasil

safety of the product.

4. Outcomes

The main objective of this study is to estimate the safety and performance of breast implants with a textured surface, and of breast implants with polyurethane foam-coated surface of the brand Silimed® already available in the market.

4.1. Primary Outcomes

- Estimate the known short-term and long-term risk / adverse event rate for each of the two types of implants of the brand Silimed®.
- Estimate the unexpected short-term and long-term risk / adverse event rate for each of the two types of implants of the brand Silimed®.

4.2. Secondary Outcomes

- Estimate the performance of the implants through the satisfaction and quality of life after breast implant of the brand Silimed®.

5. Methodology

5.1. Designing

Phase IV clinical trial, open, non-randomized (or quasi-experimental) prospective trial.

5.2. Location

This study will be conducted only in one Research Center, in a doctor's office located at [name].

5.3. Study Participants

Participants will be selected consecutively from attendance at participating center, conducted within the recruitment period. The recruitment period will last until the planned minimum sample number is reached, unless the project is interrupted for security reasons. Study participants will be invited to participate in the first medical evaluation after they have performed the implantation

Silimed Indústria de Implantes Ltda

[name]

[contact] [contact]

www.silimed.com.br • [contact] • facebook: silimed international/brasil

procedure and the eligibility criteria described below should be applied.

5.3.1. Inclusion Criteria

Inclusion criteria: (1) provide free informed consent, (2) female at birth, (3) 18 years or older, (4) have received breast implant(s) for indication of primary augmentation up to 14 days prior, (5) have received breast implants with a textured surface or breast implant with a polyurethane foam-coated surface of the brand Silimed®, (6) ability to comply with the protocol for the entire follow-up time.

5.3.2. Exclusion Criteria

Exclusion criteria: (1) secondary breast augmentation, (2) gestation or breastfeeding, medicines that increase the risk of immediate postoperative complications (e.g., medicines that interfere with coagulation), (3) advanced fibrocystic disease at the time of implantation, (4) neoplasia of any type not yet treated or being treated at the time of implantation, (5) infection in activity not yet treated or in treatment at any site at the time of implantation, (6) reporting or recording of adverse reactions or intolerance to polyurethane or silicone prior to implantation, (7) immune diseases that affect active or treating connective tissue (e.g., lupus erythematosus, discoid lupus, scleroderma, etc.) at the time of implantation, (8) signs of inflammation of the breast or implant site at the time of implantation, (9) high surgical risk or complications in the immediate postoperative period prior to implantation, (10) record or report of use of illicit drugs or medications that increase the risk of immediate postoperative complications (e.g., medicines that interfere with coagulation), (11) may not have participated in another clinical trial up to 6 months prior to implantation, (12) any other condition that, based on the opinion of the investigator or designee, may prevent the provision of informed consent, renders study participation unsafe, compromises the adherence to the protocol, complicate the interpretation of data from the study outcome, or otherwise interfere with the achievement of study objectives.

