- Capsular contracture (Baker's classification - check below): Capsular contracture occurs when the collagen fiber capsule shrinks, tightens and compresses the breast implant. Its identification and classification can be conducted during the medical evaluation by inspection and physical examination. [31,32]
- Wound dehiscence: opening of an incision that has been surgically closed. Identified during medical inspection and evaluation.

Silimed Indústria de Implantes Ltda

[name]

[contact] [contact]

www.silimed.com.br • [contact] • facebook: silimed international/brasil

- Delay in surgical wound healing: Too long progression in wound healing; The surgical wound does not heal normally or takes longer than expected. Defined as requiring additional care (e.g. dressings or additional treatment) after 7 days of implantation.
- Displacement: movement of the implant from the original location or appropriate position, due to gravity, capsular contracture, muscle traction, healing forces or implant weight. It can be detected on inspection or physical examination.
- Breast pain: pain in the scar, in the breast or adjacent structures, and may be irradiation of a breast pain.
- Wrinkle: Unnatural nodular appearance that may occur on the side of the breast or underneath it. It can be identified by inspection and clinical evaluation.
- Extrusion: displacement of the implant through a rupture of the skin or through the surgical wound with the tendency of the original implant to exit the implant.
- Galactorrhea: spontaneous flow of milk from the breast, not associated with gestation and delivery, or breastfeeding. It can be both informed by the patient and visualized during inspection and medical evaluation.
- Hematoma: rupture of blood vessels followed by collection of blood and possibly clot formation may occur in structures adjacent to the implant, especially soon after implantation. Hematoma is spontaneously absorbed. They may require surgical drainage because of their size, location, severity or because of possible undesirable clinical consequences. The need for drainage will be assessed clinically on a case-by-case basis. Identified during medical evaluation and physical examination, occasionally identified through imaging tests such as ultrasound.
- Hypoesthesia: reduced local sensitivity, both for pain and other sensations, usually reported by the patient during the physical examination.

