Visit 3: 180 days after implantation (window of + or - 30 days)	FORM 04 - Date of visit FORM 08 - Rosenberg self-esteem scale and patient satisfaction FORM 09 - Evaluator's satisfaction regarding the aesthetic result FORM 10 - BEQ - Brazil FORM 11 - Questions

Visit 4: 365 days after implantation (window of + or - 30 days))	FORM 04 - Date of visit FORM 08 - Rosenberg self-esteem scale and patient satisfaction FORM 09 - Evaluator's satisfaction regarding the aesthetic result FORM 10 - BEQ - Brazil FORM 11 - Questions
Visits 4t, 5t, 6t, 7t, 8t, 9t, 10t, 11t, 12t: 1,5; 2,5; 3,5; 4,5; 5,5; 6,5; 7,5; 8,5; 9,5 years after inclusion (window of + or - 60 days)	FORM 13- Telephone Contact
Visits 5, 6, 7, 8, 9, 10, 11 and 12: 2, 3, 4, 5, 6, 7, 8, 9 years after inclusion (window of + or - 60 days)	FORM 04 - Date of visit FORM 08 - Rosenberg self-esteem scale and patient satisfaction FORM 09 - Evaluator's satisfaction regarding the aesthetic result FORM 10 - BEQ - Brazil FORM 11 - Questions
Visit 13 – Final Visit: 10 years after implantation (window of + or - 60 days) / Early withdrawal	FORM 04 - Date of visit FORM 08 - Rosenberg self-esteem scale and patient satisfaction FORM 09 - Evaluator's satisfaction regarding the aesthetic result FORM 10 - BEQ - Brazil FORM 11 - Questions FORM 17 - End of study
Extra Visit	FORM 11 - Extra visit
Conditionals	FORM 14 - Medical History FORM 15 - Concomitant Medication FORM 16 - Adverse Event FORM 17 - End of study FORM 18 - Deviation

Silimed Indústria de Implantes Ltda

[name]

[contact] [contact]

www.silimed.com.br • [contact] • facebook: silimed international/brasil

The procedures for each data collection file can be performed on different dates as long as they are performed within the specified window of each visit.

Visit 1: The following procedures will be performed – 14 days after implantation (window of + or - 7 days):

- Identification of potential research participants
- Reception interview.
- Reading, acceptance and signature of the Informed Consent Form (ICF).
- Completion of the Research Inclusion Questionnaire (QIP).
- Completion of clinical history and complete physical examination.
- Application of patient's and evaluator's quality of life and satisfaction questionnaires.
- Delivery of the adverse event diary and guidance on its use and completion.
- Scheduling the return to the research center, 60 days after implantation.

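### Exclusion criterion 9 contradicts itself on timing and leaves room to exclude women for early complications that belong to the primary outcome

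*Combined protocol and SAP*

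**What the plan says.** Criterion 9 in section 5.3.2 excludes "high surgical risk or complications in the immediate postoperative period prior to implantation". The Executive Summary has the same words, so neither version settles the other.

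Enrolment follows surgery. Section 5.3: "Study participants will be invited to participate in the first medical evaluation after they have performed the implantation". Inclusion criterion 4 (section 5.3.1) requires a woman to "have received breast implant(s) for indication of primary augmentation up to 14 days prior". Section 6.3 places the eligibility evaluation after consent. It includes a breast examination and axillary temperature, and women found ineligible at that appointment are referred elsewhere.

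Section 4.1 gives the first primary aim: "Estimate the known short-term and long-term risk / adverse event rate for each of the two types of implants". Section 5.5 makes adverse events the primary outcome. Its list of expected events says that haematoma "may occur in structures adjacent to the implant, especially soon after implantation", and it defines delayed healing by a need for additional care beyond day 7.

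Two neighbouring criteria bear on the point:

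- Criterion 10 in section 5.3.2 covers "record or report of use of illicit drugs or medications that increase the risk of immediate postoperative complications", with no time limit. The Executive Summary limits it to use before implantation. A fragment of the same criterion also sits inside criterion 2 in section 5.3.2.
- Criterion 12 allows exclusion, on the investigator's opinion, for conditions that "complicate the interpretation of data from the study outcome, or otherwise interfere with the achievement of study objectives".

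**The concern.** Whoever applies the exclusion list already knows how the first days after surgery went. A criterion that names postoperative complications, applied at that moment, can make eligibility depend on the outcome that the study is meant to estimate.

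A woman excluded in this way contributes neither her early event nor anything that happens to her later, and the analysis cannot put her back. If the women excluded are those with early complications, the short-term risk in the remaining cohort is too low. Section 13 expects safety similar to or better than published data, so an error in this direction would favour the expected conclusion.

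**Working it through.** The plan states no figure on this point, so there is none to reproduce. The check is first one of wording and timing, then an illustration on stated assumptions.

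**Timing**

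1. Inclusion criterion 4 puts entry at up to 14 days after implantation. The Visit 1 description in section 6.4 instead reads "14 days after implantation (window of + or - 7 days", that is day 7 to day 21. On either version, screening comes after surgery.
2. Haematoma is described as typical of the time soon after implantation, and delayed healing can be met once day 7 has passed. Both can be present at or before Visit 1.

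**Two readings of criterion 9**

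- Reading A: a complication that has occurred after the implant operation excludes the woman. This needs the closing time words to be ignored.
- Reading B: high surgical risk, or high risk of early complications, judged before implantation, excludes her. This needs complications to be read as risk of complications.

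Neither reading fits every word of the clause, and no other section chooses between them.

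**Illustration under reading A**

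The documents give no early rate, so the inputs below are assumptions. Let q be the share of women with an event before screening, all of whom are excluded.

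- Women lost per 350 otherwise eligible = 350 × q. For q = 1%, 2%, 3% and 5% this is 3.5, 7, 10.5 and 17.5.
- For a true cumulative risk T, the observed risk is (T − q)/(1 − q). Take T = 31.0% (any complication, textured surface, augmentation, 7 years, table in section 2.3). With q = 1%: 0.30/0.99 = 30.3%. With q = 5%: 0.26/0.95 = 27.4%. The shift is −0.7 to −3.6 points. The 95% half-width at n = 350 is 1.96 × √(0.31 × 0.69/350) = 0.0485.

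The proportional effect is larger for events confined to the early period. Let r be the true early risk and s the share of those women affected by Visit 1 and excluded. Observed risk = (r − rs)/(1 − rs).

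- r = 2%, s = 0.5: 0.01/0.99 = 1.01%
- r = 10%, s = 0.25: 0.075/0.975 = 7.69%
- r = 10%, s = 0.5: 0.05/0.95 = 5.26%
- r = 10%, s = 0.75: 0.025/0.925 = 2.70%

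**How much of this is due to criterion 9**

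Section 5.5.1 registers adverse events from the signing of consent. Suppose the affected women are enrolled but their pre-consent events go unregistered. The observed risk is then r − rs, which for r = 10% and s = 0.5 is 0.10 − 0.05 = 5.0%, against 5.26% if they are excluded. Under that recording rule the fall from 10% to about 5% happens whatever criterion 9 says. Criterion 9 causes the full loss only where those events would otherwise be registered, for example because they are still open at Visit 1. Section 5.5.1 does not clearly say whether such events are registered.

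**The case against.** The strongest defence is that reading A is not the natural one. The clause opens with high surgical risk and closes by placing itself before implantation. Criterion 10 speaks of drugs that raise the risk of early complications, not of complications that have occurred. Criteria 5 and 8 limit infection and breast inflammation to the time of implantation, which would make little sense if criterion 9 excluded for postoperative infection. This stands: reading B is at least as plausible, and under it no woman is lost directly. It does not close the point, because the contradiction remains and the list is applied by someone who can see the early complications.

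FORM 02, completed at Visit 1, should show such exclusions. However, the minimum indicators in section 5.12 do not include a count of excluded women by reason.

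A reader might go further in several directions that the documents do not support:

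- That criterion 9 halves the reported early risk. The inputs are assumed, and nearly the same fall follows from recording events only from consent.
- That criterion 10 excludes women treated for an early event. It covers only drugs that increase the risk of early complications, and the documents name no treatment for an early event that would qualify.
- That criterion 12 is aimed at early complications. It is a general discretion clause; it only leaves room for such use.
- That the bias differs by implant surface, or carries through to later contracture. The study is unmasked, and section 2.3 lists infection prophylaxis among measures that may reduce contracture, but neither step is shown or quantified.
- That seroma, dehiscence and infection are lost in the same way. The documents tie only haematoma and delayed healing to the early period.

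**Conclusion.** The point holds as an ambiguity that should be fixed, with moderate confidence. Criterion 9 contradicts itself in both places where it appears, and one of its open readings selects women on the primary outcome. It would be wrong to say that the plan does exclude women with early complications; the documents show only that it could be applied that way.

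If it were, short-term risk would be biased downward by an amount that the documents do not allow to be estimated. The figures above are illustrations: they assume reading A, an early rate that is not in the documents, and exclusion of every affected woman. They also overlap with the effect of recording events only from consent.

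**What to change.** In the Executive Summary, section 5.3.2 and FORM 02:

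1. Reword criterion 9 to refer only to risk assessed before implantation, for example: *high surgical risk, or high risk of early postoperative complications, as assessed before implantation*.
2. Add: *An adverse event that arises after implantation does not by itself make a woman ineligible.*
3. Reconcile criterion 10 in section 5.3.2 with the Executive Summary by restoring the limit to use before implantation, and delete the stray copy inside criterion 2.
4. Keep the consent, safety and adherence parts of criterion 12. State only that the part on interpretation of outcome data may not be used to exclude a woman because of an early adverse event. Limiting the whole criterion to the time before surgery would go too far: it would also remove exclusion for later conditions that make participation unsafe or compromise adherence.

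The cost is an edit to the criteria list and one form, with no added visits, staff or participants. The small downside is that reported early event rates may be slightly higher. The change does not recover events that began before consent; that has to be settled separately in section 5.5.1.
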